1.3 Summary of Risk Management

The assessment of the risk of dabrafenib, and suggestions for management of risk, is based on non-clinical data and clinical data from an integrated safety population of 578 adult subjects with melanoma receiving 150 mg dabrafenib BID.

Dermatological effects: Epidermal hyperplasia (acanthosis) and hyperkeratosis of the skin was seen in dogs and in rats. In clinical studies hyperkeratosis (29%), skin lesions including actinic keratosis (7%) and seborrhoeic keratosis (7%), palmar-plantar erythrodysesthesia (PPE) syndrome (13%), rash (18%) and cutaneous squamous cell carcinomas (cuSCC) including keratoacanthomas (KA) (9%) have been observed. Most events were Grade 1 with the exception of cutaneous squamous cell carcinomas, which were predominantly Grade 3.

Dermatological changes are being monitored in subjects through interim medical history, assessment of adverse events and physical examination including examination of the skin. Guidelines on management of hand foot skin reactions (HFSR)/ PPE syndrome and skin rashes have been provided, with stopping criteria for persistent National Cancer Institute Common Terminology Criteria for Adverse Events, version 4.0 (NCI CTCAEv4.0 or higher) NCI-CTCAE Grade 2 or Grade 3 HFSR toxicity. Treatment of SCC, KA and keratotic lesions should occur based upon institutional practice. Dose interruptions or modifications are usually not required for SCC/KA.

Ophthalmology effects: Eye effects including blurred vision (2%), uveitis/iritis (<1%), eye pain (<1%), visual impairment (<1%) and reduced visual acuity (<1%) have been observed in clinical studies to date, with all events Grade 1 or 2. An ophthalmologic consult is required for subjects developing symptoms associated with uveitis including blurry vision, eye pain or erythema.

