Pyrexia: In clinical studies, pyrexia was one of the most frequently occurring AEs (27%), most of which (64%) were considered to be related to study treatment. Events were primarily Grade 1 (55%) or Grade 2 (39%) in severity. The majority of events occurred early during study treatment, with a median time to onset of 1st occurrence of 3 weeks, and most cases (74% of first occurrences) were of short duration (≤5 days). The majority of subjects with pyrexia were managed without dose interruption or dose reduction. Across dabrafenib studies, all SAEs of pyrexia, influenza-like illness, cytokine release syndrome, and systemic inflammatory response syndrome underwent clinical review for the identification of serious non-infectious febrile events, with complications of severe rigors, hypotension, dehydration, or renal failure in the absence of another identifiable etiology (i.e., infection). Subjects should be evaluated for signs and symptoms of infection and work up considered as clinically indicated. Dabrafenib must be held for fever of 38.5C or higher, and blood samples for an absolute neutrophil count (ANC) and serum creatinine must be drawn in the setting of fever. Subjects with fever should have a medical evaluation including measurement of blood pressure. Cases of fever with severe rigors or fever with hypotension should be reported as SAEs (regardless of whether or not hospitalization was required).

Acute Renal Failure: Acute renal failure/renal failure has been rarely reported (<1%) in subjects receiving dabrafenib, and a case of granulomatous interstitial nephritis has also been reported in a clinical trial. In some cases complicated pyrexia may be associated with renal insufficiency/renal failure, possibly secondary to dehydration or hypotension. Renal function should be monitored carefully, especially in subjects with pyrexia. Dabrafenib should be interrupted in subjects with significantly elevated serum creatinine (creatinine rise >0.5 mg/dL [44 μmol/L] above baseline or creatinine >2.0 mg/dL [177 μmol/L]).

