3.7.4.2 Renal insufficiency

Cases of renal insufficiency have occurred in adult subjects receiving dabrafenib. Prior to start of study treatment, concomitant medications must be reviewed for the potential risk of inducing nephrotoxicity and concomitant medications may be modified if clinically possible.

Guidelines regarding management and dose reduction for renal insufficiency considered to be related to study treatment by the investigator are provided in [Table 3-5](#).

Table 3-5 Mandatory Dose Modification and Required Clinical Management Guidelines for Renal function alterations

For subjects with creatinine rise \geq 50% from baseline :	Required adverse event management guidelines	Mandatory dose modification requirements
1 st occurrence	
 ● If subject has fever: treat pyrexia as per Table 5 (please note NSAIDs can induce renal insufficiency, especially in subjects with dehydration); consider IV hydration ● Pediatric nephrology consult is recommended ● Re-check within 24 hours ● If creatinine rise is < 25% from baseline: ● Monitor creatinine weekly for 4 weeks to ensure levels remain within 25% of baseline ● If creatinine rise is \geq 25% but < 50% from baseline: 
 ● Monitor creatinine at least twice weekly, can decrease frequency if creatinine rise < 25% from baseline ● Avoid nephrotoxic agents ● If creatinine rise is \geq 50% but < 100% from baseline: 
 ● Monitor creatinine at least twice weekly ● Avoid nephrotoxic agents 	
 ● If creatinine rise is < 25% from baseline: Continue dabrafenib at current dose ● If creatinine rise is \geq 25% but < 50% from baseline: 
 ● Continue dabrafenib at current dose ● If creatinine rise is \geq 50% but < 100% from baseline: 
 ● Interrupt dabrafenib ● May restart dabrafenib at reduced dose if creatinine rise returns to < 25% from baseline ● If creatinine rise is \geq 100% from baseline, permanently discontinue dabrafenib
2nd occurrence	
 ● See guidance for first occurrence 	
 ● Permanently discontinue dabrafenib

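### Protocol Section 1.3 sets an absolute creatinine trigger for interrupting dabrafenib that disagrees in threshold and scope with the percentage rule in the mandatory Table 3-5

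*Protocol*

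**What the plan says.** Section 1.3 (Summary of Risk Management), in its paragraph on acute renal failure, states: "Dabrafenib should be interrupted in subjects with significantly elevated serum creatinine". It gives two alternative triggers: "creatinine rise >0.5 mg/dL" above baseline, or "creatinine >2.0 mg/dL". It does not limit them to events attributed to study treatment, and the paragraph gives no re-check or restart condition. The section rests on non-clinical data and "clinical data from an integrated safety population of 578 adult subjects with melanoma", and describes what it offers on risk management as suggestions.

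Section 3.7.4.2 contains Table 3-5, "Mandatory Dose Modification and Required Clinical Management Guidelines for Renal function alterations". It covers renal insufficiency that the investigator considers related to study treatment. The entry condition is a creatinine rise of at least 50% from baseline, and a re-check within 24 hours is required. At a first occurrence, dosing is interrupted if the rise is at least "50% but < 100% from baseline". For restart the table says: "May restart dabrafenib at reduced dose if creatinine rise returns to < 25% from baseline". If the rise is at least "100% from baseline, permanently discontinue dabrafenib". A second occurrence also means permanent discontinuation. The table contains no absolute threshold.

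Both passages are current text. Neither refers to the other or says which prevails.

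**The concern.** The two passages measure the same laboratory value on different scales, and the scales cross. For a low baseline, a fixed rise of 0.5 mg/dL is a large percentage change; for a high baseline it is a small one. The trial enrols from 12 months to under 18 years, so one fixed rise cannot track one fixed percentage across all patients.

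The scopes differ too. A creatinine rise judged unrelated to treatment lies outside Table 3-5 but inside Section 1.3.

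At stake is whether a site can tell from the protocol when to interrupt and when to stop for good. Analysis is a secondary matter. The SAP summarises dose reductions and interruptions by pooled disease cohort (Section 2.4) and tabulates major protocol deviations (Section 2.3.2). With two rules in force, it is unclear against which one a dosing decision after a creatinine rise would be judged.

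**Working it through.** **Inputs.** From Section 1.3: rise above 0.5 mg/dL [44 µmol/L], or level above 2.0 mg/dL [177 µmol/L]. From Table 3-5: interrupt at a rise of 50% to below 100%, permanently discontinue at 100% or more. Baseline creatinine is not given for any age, so it is assumed here over 0.3 to 1.5 mg/dL.

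**Unit check.** 44/0.5 = 88.0 and 177/2.0 = 88.5 µmol/L per mg/dL. The two pairs agree apart from rounding, so the thresholds are not a unit slip.

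**Formulas.** Let b be the baseline in mg/dL.
- Section 1.3 triggers above the smaller of b + 0.5 and 2.0.
- Table 3-5 interrupts from 1.5b and permanently discontinues from 2b.
- b + 0.5 = 2b gives b = 0.5.
- b + 0.5 = 1.5b gives b = 1.0.
- b + 0.5 = 2.0 gives b = 1.5, so the 2.0 mg/dL limb acts first only above that baseline and does not help at low baselines.

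| Baseline b | Section 1.3 triggers above | Rise at that point | Table 3-5 interrupts from | Table 3-5 discontinues from |
|---|---|---|---|---|
| 0.3 | 0.80 | 167% | 0.45 | 0.60 |
| 0.4 | 0.90 | 125% | 0.60 | 0.80 |
| 0.5 | 1.00 | 100% | 0.75 | 1.00 |
| 0.6 | 1.10 | 83% | 0.90 | 1.20 |
| 0.8 | 1.30 | 62% | 1.20 | 1.60 |
| 1.0 | 1.50 | 50% | 1.50 | 2.00 |
| 1.2 | 1.70 | 42% | 1.80 | 2.40 |
| 1.5 | 2.00 | 33% | 2.25 | 3.00 |

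**Three ranges follow.**
1. b of 0.5 or less: the Section 1.3 trigger is reached only at or after the table's permanent-discontinuation threshold.
2. b above 0.5 and below 1.0: Section 1.3 triggers inside the table's interruption band, later than the table. At b = 1.0 the two interruption thresholds practically coincide.
3. b above 1.0: Section 1.3 triggers before a 50% rise, so before the table is entered.

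**Worked cases.**
- From 0.4 to 0.85 mg/dL: the rise is 0.45, and 0.45/0.4 = 112%. Section 1.3 is not triggered. Table 3-5 is entered and re-checked; if the rise is treatment-related and still at least 100%, it requires permanent discontinuation.
- From 0.4 to 0.95 mg/dL: the rise is 0.55, and 0.55/0.4 = 137.5%. Section 1.3 asks for interruption. Under the same conditions Table 3-5 requires permanent discontinuation.
- From 1.1 to 1.62 mg/dL: the rise is 0.52, and 0.52/1.1 = 47%. Section 1.3 asks for interruption. Table 3-5 is not entered as a first event and so says nothing about this child.

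**The case against.** The strongest reply is that the protocol already says where the operative rules are. Section 3.1 sends the reader to Section 3.7 for dose modification, and Section 9.2 does so for stopping criteria. Table 3-5 sits in Section 3.7 and is mandatory. Section 1.3 is an introductory summary, drawn largely from adults. Section 3.7 also has every dose adjustment made by the sponsor's medical lead with the investigator. This stands: a site would probably follow the table. It does not dispose of the point, because Section 1.3 gives numeric dosing thresholds phrased as an instruction and reaches events that the table does not cover.

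Several stronger readings are tempting and are not supported:
- *A site would keep dosing a child whose creatinine has doubled.* Section 1.3 says when to interrupt; it does not say to continue below its trigger. At low baselines the table is the stricter rule, and following it breaches nothing in Section 1.3.
- *Table 3-5 orders continuation at a 47% rise.* The table is entered at 50% or more. Its lower bands describe the value found after entry and re-check.
- *The protocol flags greater renal risk in the youngest enrolled children.* Section 1.3 places the higher risk in infants under 1 year, who are not eligible, and a correspondingly lower risk at 1 to 4 years.
- *The conflict is established for small children as such.* No document gives a baseline creatinine, so the statement is conditional on baseline, not on age.
- *Safety and discontinuation data depend on which section a site followed.* Nothing in the documents shows that any site followed Section 1.3.

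Reach is also limited. Both parts are closed to enrolment. The Amendment 11 rationale reports 85 treated and 52 completed or discontinued, leaving at most 85 − 52 = 33 on treatment in July 2020.

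**Conclusion.** The inconsistency is real and sits wholly in current text. The ordering is exact arithmetic given the baseline: at 0.5 mg/dL or less, Section 1.3 triggers only at or after the table's permanent-discontinuation threshold; above 1.0 mg/dL, it calls for interruption at rises too small to enter the table as a first event. How many patients fall in either range cannot be determined from the documents. The practical effect is probably modest, given the pointers to Section 3.7 and the closed enrolment. It is still more than clerical, because it concerns a numeric safety rule whose two statements differ in threshold and scope, and at low baselines also in the action required.

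**What to change.** Reconcile Section 1.3 with Table 3-5 so that the protocol contains one creatinine rule with one scope. One way is for Section 1.3 to cross-refer to the operative section instead of restating thresholds. The sponsor should also state whether rises judged unrelated to treatment are covered, since the two passages now differ on that. Which thresholds are right is a clinical decision on which no view is taken here. The cost is about one sentence of protocol text; the SAP needs no change.

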2 OBJECTIVES AND ENDPOINTS

Objectives	Endpoints
Primary	

 To determine the safe and tolerable dabrafenib dose(s) for chronic dosing in pediatric subjects (infants, children, and adolescents) that achieves similar exposures to the dabrafenib adult dose, in subjects with BRAF V600 mutation positive tumors 	
 Adverse Events (AEs); ECG; ECHO; changes in laboratory values and vital signs in Part 1 and Part 2. C_{max}, area under the concentration-time curve from time zero (pre-dose) to last time of quantifiable concentration [AUC(0-τ) and AUC(0-inf) of dabrafenib
Secondary	

 To characterize the pharmacokinetics of dabrafenib, and its metabolites 	
 C_τ (trough), AUC(0-t), AUC(0-τ), apparent clearance following oral dosing (CL/F) (dabrafenib only), C_{max}, t_{max} and t_{1/2} of dabrafenib and its metabolites, as appropriate

 To characterize the longer term safety and tolerability of dabrafenib 	
 AEs; ECG; changes in laboratory values and vital signs

 To assess any preliminary anti-tumor activity of dabrafenib 	
 Tumor response as defined in Appendix 2 by investigator assessment

 To determine the effect of age and weight on the pharmacokinetics of dabrafenib using a population pharmacokinetics approach 	
 CL/F, volume of distribution (V/F), absorption rate (k_a), and coefficients for significant covariates
Exploratory	

 To determine the palatability of dabrafenib in pediatric subjects 	
 Palatability questionnaire data

[figure not shown]

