Table 15-1	Evaluation of Overall Response for Subjects with Measurable Disease at Baseline.....	102

List of figures

Figure 3-1	Study Design	35
------------	--------------------	----

ABBREVIATIONS

ACCIS	Automated Childhood Cancer Information System
AE	Adverse Event
ALT	Alanine aminotransferase
ANC	Absolute neutrophil count
AST	Aspartate aminotransferase
ATP	Adenosine triphosphate
AUC	Area under concentration-time curve
AUC(0- ∞)	Area under the concentration-time curve from time zero (pre-dose) extrapolated to infinite time
AUC(0-t)	Area under the concentration-time curve from time zero (pre-dose) to last time of quantifiable concentration within a subject across all treatments
AUC(0- τ)	Area under the concentration-time curve over the dosing interval
β -HCG	Beta-Human Chorionic Gonadotropin
BID	Twice daily
BUN	Blood urea nitrogen
CI	Confidence Interval
CLIA	Clinical Laboratory Improvement Amendments
CL/F	Apparent clearance following oral dosing
C _{max}	Maximum observed concentration
CNS	Central nervous system
C _τ	Pre-dose (trough) concentration at the end of the dosing interval
CPK	Creatine phosphokinase
CR	Complete response
CRC	Colorectal cancer
CRF	Case Report Form
CRP	C-Reactive protein
CRO	Contract Research Organization
CT	Computed tomography
cuSCC	Cutaneous squamous cell carcinomas
DLT	Dose limiting toxicity
DNA	Deoxyribonucleic acid
DTIC	Dacarbazine
ECG	Electrocardiogram
ECHO	Echocardiogram
eCRF	Electronic Case Report Form
ED ₅₀	One-half the maximal effect
eGFR	Calculated Glomerular Filtration Rate
ERK	Extra-cellular signal related kinase
EU	Europe
FDA	Food and Drug Administration
FDG-PET	Fludeoxyglucose positron emission tomography
FTIH	First time in humans
G6PD	Glucose-6-phosphate dehydrogenase
GCP	Good Clinical Practice
GCPH	Global Clinical Program Head
GGT	Gamma glutamyltransferase
GI	Gastrointestinal

GSK	GlaxoSmithKline
hCG	Human chorionic gonadotropin
HFSR	Hand foot skin reactions
HGG	High grade gliomas
HIV	Human Immunodeficiency Virus
HPMC	Hydroxypropyl methylcellulose
IB	Investigator's Brochure
IEC	Independent Ethics Committee
INR	International Normalized Ratio
IRB	Institutional Review Board
ka	Absorption rate
KA	Keratoacanthomas
Kg	Kilogram
L	Liter
LCH	Langerhans cell histiocytosis
LGG	Low-grade gliomas
LLN	Lower limit of normal
LVEF	Left ventricular ejection fraction
µg	Microgram
MCH	Mean corpuscular hemoglobin
MCV	Mean corpuscular volume
MedDRA	Medical Dictionary for Regulatory Activities
mg	Milligrams
mL	Milliliter

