Clinical Activity Assessments						
Target and non-target lesion assessment	1. Must be identified at time of screening scan.	X				
Brain MRI (glioma subjects ONLY)	If an MRI of the brain was obtained within 35 days of the first dose, this can be used as screening MRI. CT with contrast allowed only if brain MRI is contraindicated). Glioma patients are not required to have CT of chest, abdomen and pelvis unless clinically indicated.	X				
LCH Assessment and LCH Scoring	LCH Assessment and LCH Scoring (Donadieu, 2004)	X				

STUDY PHASE		SCREEN	TREATMENT DAYS 1 through 21			
			Pre-dose Day 1	Pre-dose Day 8	Pre-dose Day 15	Pre-dose Day 22
VISIT		Screen				
VISIT WINDOW (\pm days)		-21	N/A	\pm 2	\pm 2	\pm 2
Performance status (Karnofsky/Lansky)	See Appendix 3	X	X	X	X	X
Study Medication						
Dispense oral study medication and assess compliance	Dispense a 2 to 4 week supply of the study medication with instructions. Record dose reductions, dose interruptions/delays, and/or dose escalations. Two doses may be administered the first day if the time between doses is in compliance with protocol Section 3.6		X			
Collection of Scans obtained prior to study						
For subjects with a diagnosis of LGG only (enrolled in all parts)	Collection of efficacy assessments (imaging scans, primarily MRI) from one of the most recent prior chemotherapy and/or targeted therapy regimen to include the baseline assessment and a time point closest to 6 months following initiation of that therapy.	To be collected within 1 month of the subject enrolling in the study, or within 1 month of this amendment being approved, whichever is the later.				

1. MRI = magnetic resonance imaging; ECG = electrocardiogram; ECHO = echocardiogram; PK = pharmacokinetic

Table 3-8 PK Sampling Table for Day 1 and Day 15 (Part 1 and Part 2)

hour	Day 1			Day 15 ^a							
	0.5	2	4	0	0.5	1	2	3	4	6	8
COLLECTION WINDOW	\pm 5 min	\pm 5 min	\pm 20 min	-30 min	\pm 5 min	\pm 5 min	\pm 5 min	\pm 20 min	\pm 20 min	\pm 20 min	\pm 20 min
Subjects \geq25 kg											
PK (2 mL samples)	X	X	X	X	X	X	X	X	X	X	X
Subjects $<$25 kg and \geq10 kg											
PK (1 mL samples)	X	X	X				X	X			
PK (2 mL samples)				X		X			X		X
Subjects $<$10 kg											

PK (1 mL samples)							X		X		
PK (2 mL samples)				X							

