5.3.3.2 Pharmacokinetic Analyses

PK parameters for dabrafenib and its metabolites for subjects in whom the full blood sampling scheme was used will be calculated with standard non-compartmental methods. The PK parameters calculated with non-compartmental methods include; AUC(0-∞) (single dose only), AUC(0-t), C_{max}, T_{max}, C_τ, CL/F (dabrafenib only), and AUC (0-τ) (where τ = 12 hours). For subjects in whom the sparse blood sample collection scheme is used, AUC(0-τ) and the average steady-state concentration will be estimated with a population PK model. Final PK parameters will be summarized and will be compared to historical adult data.

All concentration-time data may be combined and included in a population PK analysis that will examine the influence of demographics (especially age and weight) on pharmacokinetics of dabrafenib and its metabolites. PK parameters estimated in the population PK analysis will include: apparent clearance following oral dosing (CL/F), volume of distribution (V/F), and absorption rate (k_a). Data may be pooled with PK data from adult studies.

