6.5 Pharmacokinetics

6.5.1 Blood Sample Collection

Blood samples for PK analysis of dabrafenib and its metabolites, hydroxy-dabrafenib, carboxy-dabrafenib, and desmethyl-dabrafenib, will be collected at the time points indicated in [Section](#)

3.8, Time and Events Table. The actual date and time of each blood sample collection will be recorded. The timing of PK samples may be altered to ensure thorough PK monitoring (but the total number of samples and total blood volume collected will not change). Plasma concentrations of dabrafenib and its metabolites (hydroxy-dabrafenib, carboxy-dabrafenib, and desmethyl-dabrafenib) will be determined from the 2 mL blood samples collected. Plasma concentrations of dabrafenib and certain metabolites (hydroxy-dabrafenib and desmethyl-dabrafenib) will be determined from the 1 mL blood samples collected. Carboxy-dabrafenib will not be determined from the 1 mL blood sample.

Details of PK blood sample collection (including volume to be collected), processing, storage and shipping procedures are provided in the Study Procedures Manual (SPM).

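### Non-compartmental AUC(0-inf) is a primary endpoint, but Day 1 sampling ends at 4 h, too early to identify a terminal slope

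*Protocol*

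**What the plan says.** Protocol Section 2 puts Cmax, AUC(0-tau) and "AUC(0-inf) of dabrafenib" against the primary objective, which is a safe and tolerable dose giving exposure similar to that of adults. The abbreviation list defines AUC(0-inf) as "extrapolated to infinite time".

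Section 5.3.3.2 says that PK parameters "for subjects in whom the full blood sampling scheme was used will be calculated with standard non-compartmental methods", and marks AUC(0-inf) as "single dose only". The final parameters "will be compared to historical adult data". For sparsely sampled children the same section uses a population model, but only for AUC(0-tau) and the average steady-state concentration.

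Table 3-8 (Section 3.8) gives Day 1 samples at 0.5, 2 and 4 h for both weight bands from 10 kg upward. Children under 10 kg are sampled on Day 15 only (also Sections 3.1.1 and 3.1.2). Section 6.5.1 lets sample times move, "but the total number of samples and total blood volume collected will not change".

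SAP 2.9 refers PK endpoints to an earlier sponsor SAP that is not among the documents.

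**The concern.** AUC(0-inf) needs a terminal slope in order to extrapolate past the last sample. Section 1.1.2 describes a bi-exponential oral decline with a prolonged terminal phase. A schedule that stops at 4 h gives no view of that phase. A parameter with primary status may then be missing, or may be filled in from a slope that belongs to the early decline. In the second case the value could enter the planned comparison with adult data looking like a measured exposure. For children under 10 kg it cannot be derived at all by the stated method, although the primary objective names infants.

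**Working it through.** The documents give no figure of their own to reproduce here. The first step needs no model.

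**Step 1. Position of the samples**

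Inputs: oral terminal half-life 8.4 h and capsule peak about 2 h (Section 1.1.2); suspension peak 1 h (Section 1.1.4); Day 1 samples at 0.5, 2 and 4 h (Table 3-8).

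- Last sample after dosing: 4/8.4 = 0.48 terminal half-lives.
- Last sample after the peak: (4 − 2)/8.4 = 0.24 for capsules; (4 − 1)/8.4 = 0.36 for suspension.
- Samples at or after the peak: two (2 h and 4 h). For capsules, the first of these is the peak itself.

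Two points always fit a line exactly, so the slope cannot be checked for fit, and nothing in 2 to 4 h separates the early phase from the terminal phase. Using the 2.6 h intravenous half-life instead gives 4/2.6 = 1.54 half-lives, but still only two usable points. Moving three samples cannot cover absorption and also define a terminal phase.

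**Step 2. What a 2 to 4 h slope would give (illustration)**

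Disposition is A·exp(−αt) + B·exp(−βt), with β = ln 2/8.4 = 0.0825 per hour. Doses are superposed every 12 h. A, B and α are solved to match the adult steady-state values in Section 1.1.2: Cmax 1478 ng/mL, AUC 4341 ng·h/mL, trough 26.1 ng/mL. The assumed estimate is the linear trapezoid over 0, 0.5, 2 and 4 h plus C(4)/λ, where λ = ln[C(2)/C(4)]/2. The documents name no such rule.

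Worked example, zero-order input over 2 h (A = 2559, B = 37.56, α = 0.6585):

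- C(0.5) = 554, C(2) = 1457, C(4) = 410.
- λ = ln(1457/410)/2 = 0.633, so the half-life is ln 2/0.633 = 1.09 h.
- Trapezoid: 0.25×554 + 0.75×(554 + 1457) + (1457 + 410) ≈ 3514. Extrapolated part: 410/0.633 ≈ 648. Sum ≈ 4162.
- Estimate/truth = 4162/4341 = 0.96. Apparent extrapolated share = 648/4162 = 16%. True share beyond 4 h = 22%.

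The same calculation over other input shapes:

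| Shape | Peak (h) | AUC beyond 4 h | Half-life from 2–4 h slope (h) | Estimate/truth |
|---|---|---|---|---|
| First-order, assumed lag 1.0–1.5 h | 1.8–2.3 | 27–37% | 1.5–2.1 | 0.99–1.22 |
| No lag, zero-order or multi-step input | 1.8–2.3 | 18–27% | 1.1–1.7 | 0.92–1.07 |
| Peak near 1 h, several shapes | 0.8–1.25 | 17–26% | 1.1–1.6 | 0.75–0.93 |

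**Step 3. How firm these ranges are**

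The adult trough has 119% variability (Section 1.1.2). Solving again with a trough of 60 ng/mL moved three of the lagged curves from ratios of 1.05–1.20 to 0.90–1.05, and raised the share beyond 4 h to as much as 41%. Bi-exponential curves with a 2 h peak that are not matched to adult data gave 48–74% beyond 4 h, half-lives of 4.8–8.9 h and ratios of 0.98–1.38. Their Cmax/AUC was 0.12–0.17, against 1478/4341 = 0.34 in adults, so they fit the documents poorly. The table therefore illustrates the error and does not bound it.

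**The case against.** The strongest reply is that the plan already commits to a population PK model. Section 2 has a secondary objective that uses one, with CL/F as an endpoint, and Section 5.3.3.2 says sparse-sample AUC(0-tau) will come from one. Under linear kinetics a single-dose AUC(0-inf) follows from dose and CL/F. This stands. A reader might take "All concentration-time data may be combined and included in a population PK analysis" to mean that population modelling is optional as a whole, but the conditional wording applies to combining all the data. What remains is that AUC(0-inf) is assigned to the non-compartmental method and not to the model.

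Second, the handling may lie elsewhere. SAP 2.5.1, 2.5.3 and 2.9 refer to the earlier sponsor SAP, the list of changes in SAP Section 4 is partly redacted, and SAP 2.2.4 lets patients be left out of a parameter when samples are too few. This also stands. A reader might infer that a faulty value will be reported as a primary result; the documents show only that it could be. No handling rule, however, can draw a terminal slope from this schedule, and leaving patients out could empty the endpoint.

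Third, the error ratios in the table differ between a 1 h and a 2 h peak, so one might infer that capsule and suspension would be wrongly contrasted. The protocol plans a comparison with historical adult data; it does not plan a formulation comparison of AUC(0-inf).

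Finally, the error may be small on average, no hypothesis is tested (SAP 2.5.2), and most analyses are descriptive. That limits the consequence but does not make the endpoint estimable.

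**Conclusion.** The concern holds. As written, a primary endpoint rests on a terminal slope that its own sampling schedule cannot identify: 0.48 half-lives of follow-up, at most two samples at or after the peak, and no single-dose samples under 10 kg. This part rests only on the protocol's schedule and its adult PK figures.

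The parameter is therefore either not estimable or, if extrapolated from 2 to 4 h, subject to an error of unknown size and direction. On curves matched to adult data the slope gives about 1 to 2 h instead of 8.4 h. That illustration assumes adult curve shape in children, the same shape on Day 1 as at steady state, and absorption and extrapolation rules that the documents do not state.

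A reader might infer that the chosen doses are in doubt. The documents do not support that: Sections 1.2.2 and 3.1.1.1 select dose on steady-state AUC, and Day 15 is sampled to 8 h in children of 10 kg and above. The fault is confined to AUC(0-inf) and its reporting. It is modest, but worth correcting because the parameter has primary status.

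**What to change.** In Protocol Sections 2 and 5.3.3.2, keep Cmax and AUC(0-tau) as the primary PK endpoints and take non-compartmental AUC(0-inf) out of primary status. If AUC(0-inf) is still reported, use one of two forms:

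- A labelled model-based value from the population PK model already committed to. State whether Day 1 or repeat-dose clearance is used: adult AUC is 27% lower on Day 18 than on Day 1 (Section 1.1.2), so the two differ by a factor of 1/0.73 = 1.37.
- A descriptive value, with the number of subjects estimable and the percentage extrapolated. Note that this percentage depends on the same unreliable slope; in the worked example it shows 16% when the true share is 22%.

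Check the change against the earlier sponsor SAP, and declare it in SAP 2.9 and SAP Section 4.

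The cost is wording only. Enrolment is closed, so no samples can be added, and none are needed for this change. The drawback is that a listed primary parameter is relabelled after data collection, so it must be declared openly as a late change.
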